**Table 3. Motivation Study Schedule of Study Contacts**

Week	0	1	2	3	4	5	6	9	12	15	18	22	26	30	34	38	39	43	47	52
Visit	X																			
Assessment Call				X*		X*			X				X				X			X
IVR Calls			X		X		X	X		X	X	X		X	X			X	X	
BR counseling	X	X		X		X		X		X		X		X		X			X	
BA Counseling	X	X		X		X		X		X		X		X		X			X	
5Rs Counseling	X									X				X					X	
Mini-Lozenge	X								X				X			X				

\*Medication use and AE Assessments only

**Cessation Phase.** Participants who decide to quit during the first 9 months of the Motivation Phase treatment period will receive a cessation treatment. The cessation treatment includes in-person counseling sessions at Days -7, 7 and 14, and a counseling phone call on the target quit day (TQD). Participants will receive 8 weeks of medication at Day -7 (see Table 4). Two follow up assessments will occur at 28 and 56 days post TQD to assess for medication use and symptoms for the full duration of the medication schedule. *Participants who chose to receive the cessation treatment will still receive all Motivation Phase phone and IVR assessments to permit standardized assessments for all Motivation Phase participants.*

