**5Rs Motivation Counseling.** The 5Rs Motivation Counseling will be delivered in four (10-15 min) sessions over a 52-week period starting at Visit 1 and followed by three phone counseling sessions (see Table 3). Participants in the "on" condition will receive three brief phone sessions over the year to prompt processing of motives for smoking reduction or cessation. This light schedule of sessions is a reasonable burden even when paired with the other counseling conditions. The same health counselor will conduct these sessions and any other counseling interventions components (e.g., BR Counseling) with the participant. 5Rs Motivation Counseling will be similar to that described in the 2008 PHS Guideline. The health counselor and smoker will discuss: 1) Relevance of smoking to the individual; 2) Risks of continued heavy smoking; 3) Rewards of quitting and significant reduction; and 4) Roadblocks to success; and will do so on a 5) Repeated basis. The discussion will follow the general principles of MI: counselors will use strategies that are nonauthoritarian, nonconfrontational, supportive, and use open-ended questions. At the 2nd-4th sessions, the health counselor will first ask the patient to discuss his/her current feelings about smoking and then will review the patient's thoughts and attitudes shared in previous sessions. The participant will be asked to discuss any changes that have occurred over time and their relevance to making a behavior change—towards both smoking reduction and cessation goals. If a participant has stopped smoking, the call will be directed at reinforcing cessation.

**Cessation Phase.** Motivation Phase participants who decide to quit smoking during the 9 months of the intervention period will receive a smoking cessation treatment, delivered by their same health counselor with whom they have been working. This cessation treatment will involve 2 in-person counseling sessions and 2 phone counseling sessions (see Table 4). Participants will also receive 8 weeks of the Nicotine Patch and Nicotine Mini-Lozenge.

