*Supportive Therapy.* This intervention will comprise elements and content consistent with the characterization of intra-treatment support as contained in the PHS Clinical Practice Guideline (Fiore et al., 2008). Thus, it will involve encouragement (e.g., information that previous failure to quit is often positively related to subsequent success), a focus on short-term goals (e.g., go without smoking for 2 hours, communication of belief in the participant’s ability to quit), discussion of participant values (what the participant feels would be good and healthy for them in the long run) and how these values are congruent with cessation, emphasis on the patient and the counselor being a team, encouragement for the participant to generate a quitting strategy with the message that smokers often have a good sense of what will work for them (a client centered approach), and prompts for the participant to explore his/her feelings about quitting and feelings of optimism and concern; i.e., to use the counselor as a sounding board. Therefore, the Skill Training approach emphasizes explicit training while the Supportive intervention does not. Because these two forms of therapy may co-occur, counseling manuals will be carefully prepared so as to permit their effective integration. For instance, while the Skill Training intervention will recommend coping skills for the participant, when the participant also receives Supportive counseling s/he will be encouraged to discuss his/her feelings about the quit plan and reflect on its “fit” for his/her life.

*Medication.* All participants will receive 8-weeks of combination NRT (nicotine patch + nicotine mini-lozenge). Nicotine patch dosing will be based on current cigarettes smoked per day, per package insert: for those who currently smoke >10 cigs/day=4 weeks of 21 mg, 2 weeks of 14 mg, and 2 weeks of 7 mg nicotine patches, along with nicotine mini-lozenges; for those who currently smoke <=10 cigs/day=6 weeks of 14 mg and 2 weeks of 7 mg nicotine patches along with mini-lozenges. Mini-lozenge dosing will be based on how soon participants currently smoke after waking before their initial quit attempt and will be consistent with the package insert (4 mg for participants who smoke within 30 minutes of waking and 2 mg for participants smoke more than 30 minutes after waking).

“Breaking Addiction to Tobacco for Health (BREATHE) Study”

PI: [name], MPH, MBA; UW-CTRI Center Grant: 1P01CA180945-01.

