**Table 12. Schedule of Cessation Study Assessments**

Assessments	V1	TQD †	Call Wk 4	Call Wk 8	Call Wk 16	Call Wk 26	Call Wk 39	Call Wk 52
Sign informed consent and HIPAA	X							
Demographics	X							
Tobacco use history	X							
Tobacco dependence	X							
Medication beliefs	X		X	X				
Height, weight	X					X**		X**
Carbon monoxide	X					X*		
Current tobacco use	X		X	X	X	X	X	X
Motivation, self-efficacy and confidence	X		X	X	X	X	X	X
Withdrawal	X		X	X	X	X	X	X
Affect and pleasure	X		X	X	X	X	X	X
Self-report of medication adherence			X	X	X	X		
Safety assessment		X	X	X	X	X		
IVR assessment	X	X						

\*Participants who report abstinence at the 26-week call will be asked to come to the clinic to provide a breath sample to biochemically verify abstinence.

\*\*Participants will self-report weight at Weeks 26 and 52.

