**Table 13. Schedule of Long-Term Quitting Study Quit Phase (Initial Cessation) Assessments**

Day	-7	-1	1	3	7	14	28	56	84	112	140	182
Week	-1				1	2	4	8	12	16	20	26
Contact	V	I	I	I	C							
Assessments												
Sign informed consent and HIPAA	X											
Demographics	X											
Tobacco use history	X											
Tobacco dependence	X											
Health, mental health, and health behaviors	X											
Height, weight	X											
Carbon monoxide	X											
Current tobacco use		X	X	X	X	X	X	X	X	X	X	X
Other tobacco and medication use	X						X					X
Motivation, self-efficacy, and fatigue	X	X	X	X	X		X		X			X
Demoralization	X	X	X	X	X		X		X			X
Withdrawal	X	X	X	X	X		X					X
Pleasure	X	X	X	X	X							X
Coping skills	X				X							
Smoking context	X	X	X	X	X		X					
Positive Affect	X	X	X	X	X		X					X
Stressors	X						X					
Medication adherence and beliefs		X	X	X	X	X	X	X				
Medication safety assessment					X	X	X	X				
Adherence Factors question												

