## PROTOCOL

### “Breaking Addiction to Tobacco for Health (BREATHE) Study”

PI: [name], MPH, MBA; UW-CTRI Center Grant: 1P01CA180945-01.

Day	-7	-4	-1	1	3	7	14	28	70	112	182	
Week	-1					1	2	4	10	16	26	
Contact	V	I	I	I	I	V/C	C	C	C	C	C	
Questionnaire												
Avoidance and Inflexibility Questionnaire	X					X		X				
Medication safety	X					X	X	X				
Smoking context	X	X	X	X	X	X	X	X				

V = Visit; I = IVR assessment; C = Call;

\* = This visit is only for participants claiming abstinence.

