To facilitate safety, participants who may not be medically appropriate to take NRT will not be included in the study (e.g., hospitalized within the past month for a stroke, heart attack, congestive heart failure or diabetes). Once enrolled, follow-up protocols will assess for medication side effects and unanticipated health events at all study visits and follow-up contacts. We will recommend NRT dosage/use alterations as per good clinical practice if the patient experiences symptoms of nicotine toxicity or other troublesome side effects once they begin medication treatment. We will refer participants to their referring physician as needed. Should either excessive risk to study participants and/or lack of measurable benefit to study participants be determined, the study will be stopped and all participants notified in a manner appropriate to the nature of the risk and/or lack of benefit.

In terms of confidentiality risk, the UW-CTRI Information Technology Administrator manages the hardware, data, security, and infrastructure below the firewall. Access to the network is limited to only UW-CTRI owned and actively managed devices. All devices automatically lock and are password protected after 15 minutes of inactivity. All portable devices are encrypted for data security and no PHI is stored on local devices. All data stored on the network file server is limited by the principle of least privilege.

As stated above, no data are stored on individual computer hard drives. All data are transmitted from the point of collection to the UW-CTRI server through secure, encrypted web connection. On those rare occasions when, due to a loss of internet access or computer hardware failure, data are collected in paper forms, these forms will be stored securely in the clinic and transported personally by the case manager to UW-CTRI. No identifying data other than a participant ID number is entered on any data form. Any paper collected data are entered

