*Monitoring the progress of trials and the safety of participants.* The PIs of the Program Project will be responsible for routine monitoring of the progress of the research. This monitoring includes scheduled biweekly meetings with study staff and review of written documentation of all research projects. Data that are reviewed at these meetings include the number and type of participants enrolled, the number and reasons for exclusions from enrollment, the number of participants treated and the stage of intervention, a summary and an individual review of any unanticipated health events, and outcome data.

To facilitate participant safety, study participants must meet study inclusion and exclusion criteria. Once enrolled, follow-up protocols will assess the presence of medication side effects and unanticipated health events at all study visits and follow-up contacts. We will recommend dosage/use alterations as per good clinical practice if the patient experiences symptoms of nicotine toxicity or other troublesome side effects. We will refer patients to the study physician and/or their referring physician based on defined, regularly administered medication safety protocols. Any unanticipated health events that raise concerns (e.g., allergic reaction, symptoms suggestive of nicotine toxicity) will be immediately reported to the study physician. Such symptoms typically result in dosage changes or medication stoppage. Should either excessive risk to study participants and/or lack of measurable benefit to study participants be determined, the study will be stopped and all participants notified in a manner appropriate to the nature of the risk and/or lack of benefit.

*Plans for the reporting of unanticipated health events.* This DSMP requires that investigators notify NIH and the University of Wisconsin IRB in a timely manner of the occurrence of any unanticipated health events, which are severe, unanticipated, and possibly related to study medication or protocol.

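### Long-term Quitting Study, RR Cessation phase: the last scheduled medication-safety item (Day 28) comes 21 to 28 days before the 8-week NRT course ends, and no later item looks back

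*Combined protocol and SAP*

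**What the plan says.** Two places make a general commitment. Protection Against Risk states that "follow-up protocols will assess for medication side effects and unanticipated health events at all study visits and follow-up contacts". The Data and Safety Monitoring Plan says the same and adds that referral to a physician is "based on defined, regularly administered medication safety protocols".

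The RR Cessation medication paragraph gives all entrants 8 weeks of patch plus mini-lozenge. Table 8 has it dispensed at the Day -7 visit. Table 15 marks "Medication safety" at Days -7, 7, 14 and 28 and leaves it blank at Days 70, 112 and 182. The same table does ask about medication adherence at Day 70.

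Two parallel 8-week courses are handled differently:

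- **Motivation Study, Cessation Phase.** The products are the same: "Participants will also receive 8 weeks of the Nicotine Patch and Nicotine Mini-Lozenge". Assessments at Days 28 and 56 after the quit day are there "to assess for medication use and symptoms for the full duration of the medication schedule".
- **Long-term Quitting Study, Initial Cessation (patch only).** Table 13 marks "Medication safety assessment" at Days 7, 14, 28 and 56.

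**The concern.** The text promises side-effect questions at every contact, while the phase's own schedule stops them about halfway through dosing. The text on RR Cessation assessments refers to Table 15 for their content, and The Intervention Components says a common database guides which assessments are given at each contact. An item missing from the schedule may therefore not be prompted.

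What could be lost is non-serious side effects and dosing problems late in the course. The Safety Review Committee sees safety data by treatment condition every six months, and late-course counts for this phase could be too low in all four cells. They would also compare poorly with counts from the Motivation Study's course, which is followed to its end.

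**Working it through.** The plan gives no figure for this, so there is none to reproduce. The check is schedule arithmetic.

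**Inputs**
- Course length: 8 weeks = 56 days (RR Cessation, Medication).
- Dispensing: Day -7 (Table 8). The first day of use is not stated for this phase, so both Day -7 and the target quit day (Day 0) are tried. The Motivation cessation phase and Modern Usual Care start the patch on the quit day, which makes Day 0 the likelier reading.
- Last safety item: Day 28 (Table 15).

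**Uncovered part of the course** (course end = start + 56; gap = course end - 28)

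| Start | Course ends | Gap after Day 28 | Share of course |
|---|---|---|---|
| Day -7 | -7 + 56 = Day 49 | 49 - 28 = 21 days | 21/56 = 37.5% |
| Day 0 | 0 + 56 = Day 56 | 56 - 28 = 28 days | 28/56 = 50% |

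**Does another scheduled contact fill the gap?**
- RR Cessation follow-up calls at Days 70, 112 and 182: no safety item (Table 15).
- Preparation treatment contacts, which carry the Reduction arm's later safety items: these end on entry to RR Cessation.
- Standard Assessment Staff Calls at Months 2, 4, 7 and 10 and the Month 14 call: no safety item in Table 14.
- Counseling calls at Week 6 (Day 42) and Week 8.5 (Day 60): held in three of the four cells, with no safety item scheduled.
- Brief-Information-only cell: no RR Cessation contact at all between Day 28 and Day 70 (Table 8).

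**Patch dose in the uncovered weeks**
- More than 10 cigarettes/day: 4 weeks of 21 mg, ending on Day 28 (quit-day start) or Day 21 (Day -7 start). The uncovered weeks are the step-down.
- 10 or fewer: 6 weeks of 14 mg, ending on Day 42 or Day 35. Part of the uncovered period is at the starting dose.
- The mini-lozenge is supplied for the full 8 weeks in both groups.

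**What the proposed items would reach**
- Day 70 item: 70 - 56 = 14 to 70 - 49 = 21 days after the last dose; recall 70 - 28 = 42 days.
- Day 42 prompt: remaining unchecked tail 49 - 42 = 7 or 56 - 42 = 14 days, in three cells.

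**The case against.** The best reply is that the general commitment already governs: investigators must comply with the Data and Safety Monitoring Plan, and a table listing the form at some contacts does not cancel that duty. Part of this stands. A reader might infer that nobody asks about side effects after Day 28, and the documents do not show that. A blank cell shows only that the item is not scheduled. The mismatch remains, because staff are directed to Table 15 and to database prompts.

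The second reply is low risk, and it largely stands. The patch is stepping down for heavier smokers. Entrants were already given the patch in Initial Cessation. Under Protection of Human Subjects, a medication stopped for NRT symptoms is not prescribed again in a later phase. Recycling entrants may, however, be new to the mini-lozenge.

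Third, long intervals between safety items are common here. In Table 12 the "Safety assessment" row goes from Week 8 to 16 to 26. That is fair: the interval is not distinctive, but the missing closing check is.

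Three further inferences should be resisted:

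- **Missed events.** With about 270 expected entrants, one could compute 270 x 21 = 5,670 to 270 x 28 = 7,560 person-days. These are days of supply, not use. The plan gives no usage rate after Day 28, and nothing here estimates events.
- **Bias among cells.** All four cells share the Table 15 schedule, so the gap does not of itself favor any of them.
- **Every other NRT course is covered to its end.** This cannot be said of Preparation Controls. The note to Table 6 stops all treatment on relapse, while Study Design and the RR Preparation text have Controls continue their remaining medication. That is a separate inconsistency and should be raised separately.

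**Conclusion.** The point holds as a mismatch between the text and the schedule, with minor consequences. In the RR Cessation phase no scheduled safety item covers the last 21 days (Day -7 start) or 28 days (quit-day start) of a 56-day course, and none looks back later. The range depends only on the unstated first day of use. The omission looks unintended, since the Motivation Study's matching course is checked at Day 56 and no reason is given for the difference.

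No efficacy endpoint, power figure or error rate is affected. Serious events reported on calls are examined within 72 hours. The change is worth making because it costs almost nothing and brings the schedule closer to the commitment.

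**What to change.** 1. Add the existing Medication safety item to Table 15 at the Day 70 call, with recall since Day 28. All four cells receive this call and it already carries the adherence questions. This closes late-course event capture.
2. Prompt the same item at the Week 6 (Day 42) counseling call in the three cells that have it, so that dose advice is possible while participants are still dosing.
3. Compare safety by RR Cessation condition using only the time points common to all four cells: Days -7, 7, 14, 28 and 70. Otherwise the extra Day 42 question could raise counts in three cells.
4. Keep the call at Day 70. The RR Cessation text lists it as Month 2, but Tables 8 and 15 and Secondary Aim 2 place it at Week 10, and moving it would change that outcome's time point.

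The cost is slightly longer calls and a database prompt, with no new contacts. Two limits remain. The Day 70 item relies on 42-day recall and comes too late for dose advice. Brief-Information-only participants still have no in-course item after Day 28.

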**“Breaking Addiction to Tobacco for Health (BREATHE) Study”**

PI: [name], MPH, MBA; UW-CTRI Center Grant: 1P01CA180945-01.

into the computer immediately upon receipt at UW-CTRI and the paper document is disposed of securely. Consent forms are obtained in paper copy; these forms contain the participant name and signature. These are retained in secure files at the clinic where they are collected and then transported to the UW-CTRI office, where they are securely stored.

Finally, no publications or presentations resulting from this research will contain any identifying information about individual participants.

Potential Benefits of the Proposed Research to the Participants and Others

The potential benefits for smokers participating in the Motivation Study include the chance to reduce their smoking and make a quit attempt sooner than they otherwise would have. Benefits for all research participants include the chance to receive smoking cessation counseling and pharmacotherapy at no cost—two evidence-based treatments which can double a smoker’s odds of quitting successfully. Considerable research has demonstrated that, whenever a smoker quits successfully, health benefits occur. In addition, quitting smoking reduces the burden of secondhand smoke exposure to others. Finally, the benefit of reduced healthcare costs, morbidity and mortality related to smoking is a societal benefit from quitting smoking.

The health and economic benefits to the individual and society greatly outweigh the risks in terms of discomfort, side effect of medication and loss of confidentiality.

Importance of the Knowledge to be Gained

These research studies will develop new treatments and determine whether treatment packages engineered using Phase-Based intervention components and the MOST approach are more effective and more cost-effective than usual care treatment for smoking cessation. This information could lead to the provision of tested treatment packages that a health system can implement for smoking cessation, as the cornerstone of a chronic care treatment for smoking. Further, this research will identify treatment mechanisms via which the treatments exert their effects. Such knowledge could be helpful in developing new treatment packages and for personalizing treatment based on which treatments work for various groups of smokers. Finally, the studies will test methodologies designed to more rapidly develop effective interventions, test them and bring them into clinical use, considerably shortening and improving the methodology for research translation into practice.

As outlined above, the risks of this study are minimal and limited to the discomfort of quitting smoking, generally mild side effects of medication and small risk of breach of confidentiality. The potential study impact on increased numbers of smokers across clinical settings nationally far outweigh these risks.

Data and Safety Monitoring Plan

The following Data and Safety Monitoring Plan (DSMP) pertains to all research to be supported under the National Institute of Health (NIH) Program Project Award. This plan comprises not only the research conducted directly by the University of Wisconsin Center for Tobacco Research and Intervention (UW-CTRI) researchers, but also research conducted by other investigators who are supported by these funds. All investigators must agree to comply with the procedures outlined in this DSMP. This DSMP does not reduce any investigator’s obligation to comply with the requirements of the UW Institutional Review Board (IRB) or the IRB of any collaborating organizations.

“Breaking Addiction to Tobacco for Health (BREATHE) Study”

PI: [name], MPH, MBA; UW-CTRI Center Grant: 1P01CA180945-01.

*Monitoring the progress of trials and the safety of participants.* The PIs of the Program Project will be responsible for routine monitoring of the progress of the research. This monitoring includes scheduled biweekly meetings with study staff and review of written documentation of all research projects. Data that are reviewed at these meetings include the number and type of participants enrolled, the number and reasons for exclusions from enrollment, the number of participants treated and the stage of intervention, a summary and an individual review of any unanticipated health events, and outcome data.

To facilitate participant safety, study participants must meet study inclusion and exclusion criteria. Once enrolled, follow-up protocols will assess the presence of medication side effects and unanticipated health events at all study visits and follow-up contacts. We will recommend dosage/use alterations as per good clinical practice if the patient experiences symptoms of nicotine toxicity or other troublesome side effects. We will refer patients to the study physician and/or their referring physician based on defined, regularly administered medication safety protocols. Any unanticipated health events that raise concerns (e.g., allergic reaction, symptoms suggestive of nicotine toxicity) will be immediately reported to the study physician. Such symptoms typically result in dosage changes or medication stoppage. Should either excessive risk to study participants and/or lack of measurable benefit to study participants be determined, the study will be stopped and all participants notified in a manner appropriate to the nature of the risk and/or lack of benefit.

*Plans for the reporting of unanticipated health events.* This DSMP requires that investigators notify NIH and the University of Wisconsin IRB in a timely manner of the occurrence of any unanticipated health events, which are severe, unanticipated, and possibly related to study medication or protocol.

Because this study involves pharmaceutical agents, in the event of an unanticipated health event that might be related to drug use, both the FDA and the manufacturer will also be notified within 5 days of investigators becoming aware of the event. Examples of a serious unanticipated health event would be untoward occurrences related to study participation that result in death, are life-threatening, require hospitalization or prolonging of existing hospitalization, create persistent or significant disability/incapacity, or involve congenital abnormality/birth defects. Unanticipated health events would also include less serious problems that merit reporting because they are severe, unanticipated, and possibly related to study participation. All serious unanticipated health events, including those reported during scheduling and follow-up calls, will be examined within 72 hours and reported as required by IRB, NIH and/or FDA rules. The PIs will be responsible for the accurate documentation, investigation, and follow-up of all study-related unanticipated health events.

Unanticipated health event assessment, recording, reporting, and investigation will be accomplished through staff training, structured/standardized assessments of untoward occurrences/events, and regular monitoring by study physicians and other study investigators. The Project Leaders and the Program Project Co-Principal Investigators have ultimate responsibility for ensuring that unanticipated health events are detected and reported in a timely manner. Additionally, the IRB will receive an annual report of all serious unanticipated health events and unanticipated health events meeting the criteria listed above.

“Breaking Addiction to Tobacco for Health (BREATHE) Study”

PI: [name], MPH, MBA; UW-CTRI Center Grant: 1P01CA180945-01.

*Plans for assuring that any action resulting in a temporary or permanent suspension of an NIH-funded clinical trial is reported to the NIH grant program director responsible for the grant.* The NIH grant program director will be notified within 5 days if the Program Project PIs deem it necessary to suspend a clinical trial. In the case of a temporary suspension, the Program Project Co-Principal Investigators and Project Leader will develop a plan for continuation of the study and discuss this plan with the NIH grant program director in a reasonable time frame.

*Plans for assuring data accuracy and confidentiality and protocol compliance.* The Project Leader, supported by staff, will refine and monitor existing protocols for assuring data accuracy and protocol compliance. Data from their compliance reviews will be shared with the Program Project PIs. Such protocols will include data verification and protocol compliance checks. The Data Manager and IT Manager will also be responsible for ensuring that the data for the project are securely stored, that storage is in compliance with University and federal regulations and that no unauthorized persons have access (electronic or physical) to any participant-identifiable data. The PI’s will ensure that HIPAA regulations and guidelines are currently implemented and all study staff have completed approved human subjects and HIPAA training programs. The.

Safety Review Committee

In addition to the protections outlined in the Program Project-wide DSMP (above), all three studies conform to the NIH definition of a clinical trial. All of the trials in this P01 application are Phase IV clinical trials that are not multicenter in nature (the projects are testing existing interventions delivered through new methods to determine population effectiveness). The DSMP specifies overall monitoring that will be conducted by the PIs for all projects. Their responsibilities include timely reporting of unanticipated health events and serious unanticipated health events. Every 6 months, the Program Project-wide Safety Review Committee will convene to review the overall safety data, as well as data on safety summarized by treatment condition. The objective of these reviews will be to determine whether continued conduct of the trial poses no undue risk for participants.

The Program Project-wide Safety Review Committee will be chaired by [name], leader of the Palliative Care and Supportive Oncology Group at the UW Carbone Cancer Center. [name] is a very experienced physician and clinical trial researcher with no involvement in any of this P01’s research activities. [name] will be joined on the committee by [name] and [name]. [name] is a practicing general internist and has collaborated on clinical trials with UW-CTRI in the past. [name] has served on independent Data and Safety Monitoring Boards for Phase II and III trials involving a nicotine vaccine. Neither has direct involvement with any of this P01’s research activities. UW-CTRI’s data staff will provide support for these reviews including summaries of safety data by treatment condition. The PIs will participate in these reviews and take lead responsibility for implementing any recommended changes in procedure or protocol.

“Breaking Addiction to Tobacco for Health (BREATHE) Study”

PI: [name], MPH, MBA; UW-CTRI Center Grant: 1P01CA180945-01.

